The continuous endpoints at Week 12 will be analyzed in a similar way as the secondary endpoints at Week 24.

The binary endpoints will be analyzed in the similar way to the primary efficacy endpoint. The safety variables, including adverse events (AEs), laboratory parameters, vital signs, electrocardiogram (ECG), and physical examinations will be summarized using descriptive statistics.

- **Missing data handling**

For continuous endpoints, missing data due to lack of efficacy will be imputed using WOCF approach and missing data not due to lack of efficacy will be imputed using a multiple imputation method, which will use all participants except those who have taken the highly influential prohibited medications and/or highly influential rescue medications and excluding patients who discontinue due to lack of efficacy. For binary endpoints, missing data will be considered as non-responder.

In addition to the missing data handling approaches specified above, the reason and pattern of missing data will be carefully examined, and tipping point analyses and additional sensitivity analyses will be performed.

- **Multiplicity considerations**

A multiplicity hierarchical testing will be proposed to control the overall Type-I error rate for testing the primary endpoint, selected patient-reported outcome (s) (PRO) and the other key secondary endpoints. The study is considered positive when the primary endpoint achieves statistical significance. Detailed multiplicity adjustment procedure for the efficacy endpoints will be described in the study SAP.

- **Planned database lock date**

[figure not shown]
A primary database lock will be performed when all randomized participants have completed their treatment phase. Final analyses in the clinical study report (CSR) will be based on all data collected up to this database lock.

The database will be updated at the end of the study for all participants to include the post-treatment follow-up information and updates for the events previously ongoing at the time of the primary lock. Additional data between this database lock and last participant completing last visit will be summarized in a CSR addendum.

Data Monitoring Committee: No

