Secondary 
Proportion of participants receiving rescue therapy for chronic induced ColdU during the planned treatment periodProportion of participants with cold exposure triggered urticaria requiring emergency medical care visit or treatment with epinephrine (at provocation test and/or at home)	These binary endpoints will be summarized using the count and percentage of participants.
Tertiary/Exploratory 
• [REDACTED]• [REDACTED]• [REDACTED]	

Endpoint	Statistical analysis methods
•	
•	
•	

A multiplicity hierarchical testing will be proposed to control the overall Type-I error rate for testing the primary endpoint, selected PRO(s), and the other key secondary endpoints. The study is considered positive when the primary endpoint achieves statistical significance. A detailed multiplicity adjustment procedure for the efficacy endpoints will be described in the study SAP.

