1 INTRODUCTION

1.1 STUDY DESIGN

The EFC16720 study is a 24-week, randomized, double-blind, placebo-controlled, parallel-group, multi-center study to evaluate the use of dupilumab in adults and adolescents (≥ 12 to < 18 years old) with primary acquired chronic inducible cold urticaria (ColdU) who remain symptomatic despite the use of H1-antihistamine treatment. The study is designed to test the hypothesis that dupilumab will increase the proportion of participants with a negative ice cube provocation test at Week 24 compared with placebo. A negative ice cube provocation test is defined as the absence of a confluent hive/wheal at the entire skin site of exposure after an ice cube provocation test.

The study consists of 3 periods:

- Screening period (2 to 4 weeks).
- Randomized IMP treatment period (24 weeks).
- Post IMP treatment period (12 weeks).

Chronic inducible ColdU signs and symptoms will be evaluated after the ice cube provocation test, by the Investigator (hives/wheals intensity) and participant (itch severity, skin pain, skin sensation). In addition, chronic inducible ColdU disease activity will be assessed daily by the participant using ColdUAS questionnaire in an e-diary where the participant will report his/her skin reactions (wheals and swelling), skin sensations (itching, burning, pain or feeling hot), if they have been in contact with cold temperatures that usually cause skin reactions, if they have avoided trigger exposure, and overall symptoms severity. The study will also assess the effect of dupilumab on urticaria control, participants' HRQoL and overall health status, proportion of patients with cold urticaria requiring emergency medical care visit or treatment with epinephrine and on reduction of rescue therapy.

The total anticipated number of participants randomized in the study is 78. This corresponds to approximately 39 participants who will be randomly assigned to each intervention arm:

- Dupilumab: 300 mg every q2w for adults; 200 mg q2w for adolescents ≥ 30 kg and < 60 kg at baseline or 300 mg q2w for adolescents ≥ 60 kg at baseline.
- Matched placebo.

At least 4 participants randomized in the study will be adolescents (≥ 12 to < 18 years old) who will be recruited in a few selected sites in selected countries. Randomization will be stratified by age (adolescent versus adult) and within adult group by country and background H1-antihistamine regular/daily use (Yes/No).

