
• To demonstrate the efficacy of dupilumab on primary acquired chronic inducible ColdU local signs and symptoms (hives/wheals, itch, burning sensation and pain) after provocation test• To demonstrate the efficacy of dupilumab on primary acquired chronic inducible ColdU disease activity• To demonstrate improvement in health-related quality-of-life and overall disease status and severity• To evaluate the ability of dupilumab in reducing the proportion of participants who require rescue therapy• To evaluate the proportion of participants with cold exposure triggered urticaria• To evaluate safety outcome measures	
• Proportion of participants with an improvement of ≥ 3 in UCT 4-item from baseline to Week 24 compared with placebo.• Change from baseline in local wheal intensity at the provocation site at Week 12 and Week 24 using the wheal intensity Likert scale ranging from 0 to 5 (clinician evaluation) compared with placebo• Change from baseline in local itch severity at the provocation site at Week 12 and Week 24 using the Peak Pruritus Numerical Rating Scale (NRS, score 0 to 10) (patient reported) compared with placebo• Change from baseline in local skin burning sensation at the provocation site at Week 12 and Week 24 using the peak burning sensation NRS (patient reported) compared with placebo• Change from baseline in local pain severity at the provocation site at Week 12 and Week 24 using the peak pain sensation NRS (patient reported) compared with placebo• Proportion of participants with negative ice cube provocation test at Week 12 compared with placebo• Change from baseline in cold urticaria signs and symptoms severity at Week 24 on cold exposure days as measured by ColdUAS, compared with placebo• Change from baseline in the proportion of cold urticaria sign and symptom free days at Week 24 on cold exposure days as measured by ColdUAS, compared with placebo• Change from baseline in health-related quality-of-life (HRQoL) as measured by Dermatology Life Quality Index (DLQI) in participants ≥ 16 years old, and in Children's Dermatology Life Quality Index (CDLQI) in participants ≥ 12 to < 16 years old at Week 24 compared with placebo• Change from baseline in Cold Urticaria Quality of Life (ColdU-QoL) at Week 24 compared with placebo.• Proportion of participants receiving rescue therapy for primary acquired chronic inducible ColdU during the planned treatment period compared with placebo• Proportion of participants with cold exposure triggered urticaria requiring emergency medical care visit or treatment with epinephrine (at provocation test and/or at home)• Percentages of participants experiencing treatment-emergent adverse events (TEAEs) or serious adverse events (SAEs)

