
4.4.2 Supportive secondary endpoint(s)

The change from baseline endpoints:

- Change from baseline in urticaria control test (UCT 4-item) at Week 24
- Change from baseline in local wheal intensity at the provocation site at Week 12 using the wheal intensity Likert scale ranging from 0 to 5 (clinician evaluation)

- Change from baseline in local itch severity at the provocation site at Week 12 and Week 24 using the Peak Pruritus Numerical Rating Scale (NRS, score 0 to 10) (patient reported)
- Change from baseline in local skin burning sensation at the provocation site at Week 12 and Week 24 using the peak burning sensation NRS (patient reported)
- Change from baseline in local pain severity at the provocation site at Week 12 and Week 24 using the peak pain sensation NRS (patient reported)
- Change from baseline in cold urticaria signs and symptoms severity at Week 24 on cold exposure days as measured by ColdUAS
- Change from baseline in health-related quality of life (HRQoL) as measured by Dermatology Life Quality Index (DLQI) in participants ≥ 16 years old, and in Children's Dermatology Life Quality Index (CDLQI) in participants ≥ 12 to < 16 years old at Week 24
- Change from baseline in Cold Urticaria Quality of Life (ColdU-QoL) at Week 24

The Week 12 and Week 24 values will be analyzed separately and use the same procedure as the key secondary endpoint. The endpoint change from baseline in DLQI will be summarized and analyzed in participants ≥ 16 years old who completed the DLQI at baseline. The endpoint change from baseline in CDLQI will be summarized separately in participants ≥ 12 to < 16 years old using descriptive analysis only.

The proportion endpoints below will be analyzed like the primary endpoint.

- Proportion of well-controlled participants (UCT ≥ 12) at Week 24
- Proportion of participants with an improvement of ≥ 3 in UCT 4-item from baseline to Week 24
- Proportion of participants with negative ice cube provocation test at Week 12

The two endpoints below will be summarized using the count and percentage of participants.

[figure not shown]
- Proportion of participants receiving rescue therapy for primary acquired chronic induced ColdU during the planned treatment period
- Proportion of participants with cold exposure triggered urticaria requiring emergency medical care visit or treatment with epinephrine (at provocation test and/or at home)

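### The rescue-therapy endpoint is worded as a reduction compared with placebo, but only counts and percentages are planned, so no between-arm estimate or interval is pre-specified

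*SAP*

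**What the plan says.** **Rescue therapy.** SAP 1.2, Table 1 gives the objective as "To evaluate the ability of dupilumab in reducing the proportion of participants who require rescue therapy" and the endpoint as "Proportion of participants receiving rescue therapy for primary acquired chronic inducible ColdU during the planned treatment period compared with placebo". The protocol's objectives tables (Sections 1.1 and 3) agree.

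**Emergency care or epinephrine.** In the same SAP table the objective is "To evaluate the proportion of participants with cold exposure triggered urticaria" and the endpoint is "Proportion of participants with cold exposure triggered urticaria requiring emergency medical care visit or treatment with epinephrine (at provocation test and/or at home". Neither mentions a reduction or a comparison with placebo. Only the design narrative goes further: in SAP 1.1, the sentence listing what dupilumab's effect will be assessed on includes "proportion of patients with cold urticaria requiring emergency medical care visit or treatment with epinephrine and on reduction of rescue therapy". Protocol 1.1 and 4.1 carry similar text.

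**Analysis of both.** SAP 4.4.2 says "The two endpoints below will be summarized using the count and percentage of participants". Protocol 9.4.1, Table 7 places the two endpoints in a row of their own with the rule "These binary endpoints will be summarized using the count and percentage of participants". The protocol synopsis, in its paragraph on secondary endpoints, says without exception: "The binary endpoints will be analyzed in the similar way to the primary efficacy endpoint". For the primary endpoint that means a stratified Cochran-Mantel-Haenszel (CMH) test with an odds ratio and 95% CI.

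**The concern.** For rescue therapy, the objective asks how much dupilumab changes a proportion relative to placebo, and the planned output is one percentage per arm. No difference, ratio or interval is specified. If someone later wants one, the measure, the stratification and the handling of early leavers would be chosen after the results are known.

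The plan is fuller for comparable or lesser outcomes. The other three binary secondary endpoints in SAP 4.4.2 are analysed like the primary. Common adverse events in SAP 4.7.2 get Miettinen-Nurminen risk differences with 95% CIs.

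The rescue proportion also carries some weight. The protocol's summary of changes explains that time to first rescue was dropped partly because the retained proportion endpoint was thought enough to evaluate the effect on rescue need. With small arms, two bare percentages can look like a large effect without showing how uncertain it is.

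**Working it through.** **Step 1. Set wording against analysis.**

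| Endpoint | Objective | Endpoint wording | SAP 4.4.2 and protocol Table 7 | Protocol synopsis |
|---|---|---|---|---|
| Rescue therapy | Reduce the proportion | Compared with placebo | Count and percentage | Like the primary |
| Emergency care or epinephrine | Evaluate the proportion | No comparator | Count and percentage | Like the primary |

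For rescue therapy, the analysis conflicts with the objective, the endpoint wording and the synopsis. For emergency care it conflicts with the synopsis and sits awkwardly with the design narrative, but it matches the objective and endpoint. SAP 5.3 adds rescue-medication summaries overall, by type and by days of use, all descriptive. SAP Appendix 2 (5.2) does not settle the difference.

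**Step 2. Inputs for the precision check.** The documents give no expected rescue rate and no figure to reproduce for this endpoint. The only sample size is for the primary endpoint: 39 per arm with 10% drop-out, that is 39 × 0.9 = 35.1 evaluable. I take n = 39 per arm because the efficacy population is ITT. The rescue rates are my assumption: a halving on dupilumab from placebo rates of 10% to 50%.

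**Step 3. Formulas.** With placebo rate p1 and dupilumab rate p2:

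- Half-width = 1.96 × √[p1(1−p1)/n + p2(1−p2)/n].
- Example, 30% v 15%: √[(0.21 + 0.1275)/39] = √0.008654 = 0.0930, and 1.96 × 0.0930 = 0.182. The interval is −0.150 ± 0.182, that is −0.332 to 0.032.
- Power uses the normal approximation for two proportions, with pooled variance under the null and unpooled variance under the alternative.

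**Step 4. Results.**

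| Placebo v dupilumab | Difference (points) | Half-width (points) | 95% CI (points) | Power, two-sided 0.05 | Power, two-sided 0.01 |
|---|---|---|---|---|---|
| 10% v 5% | −5 | 11.6 | −16.6 to 6.6 | 13% | 4% |
| 20% v 10% | −10 | 15.7 | −25.7 to 5.7 | 23% | 9% |
| 30% v 15% | −15 | 18.2 | −33.2 to 3.2 | 35% | 16% |
| 40% v 20% | −20 | 19.8 | −39.8 to −0.2 | 49% | 25% |
| 50% v 25% | −25 | 20.8 | −45.8 to −4.2 | 63% | 38% |

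**Step 5. Reading.** An observed halving has an interval that includes zero at placebo rates of 10% to 30% and excludes zero at 40% to 50%. The 40% v 20% case is marginal. With 35 per arm, every half-width grows by √(39/35) = 1.056, and 19.8 becomes about 20.9, which just includes zero.

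**The case against.** - **The protocol chose this on purpose.** Table 7 separates these two endpoints from the binary endpoints analysed like the primary, and the SAP carries that over. This stands. A reader might infer that the SAP introduced the gap, but the documents do not support that. The conflict is between Table 7 and SAP 4.4.2 on one side, and the endpoint wording and the synopsis on the other.
- **Emergency care is descriptive by definition.** This largely stands. A reader might extend the point to both endpoints, but the emergency-care objective and endpoint contain no comparison or reduction. The design narrative alone is too little to say otherwise.
- **The objective can still be answered.** It is tempting to say that it cannot, but counts by randomised arm are enough for a crude difference and interval. What is missing is a pre-specified estimate.
- **One scenario can mislead.** At 30% v 15% it looks as though the trial could not establish a halving of rescue use. The 40% v 20% and 50% v 25% rows show that this depends on the assumed rate.
- **The primary method does not transfer directly.** This stands and shapes the fix. The primary analysis reports an odds ratio, not a difference. Three regions by two background-therapy levels give six strata for 78 participants, 13 on average. In SAP Table 4, systemic corticosteroids confirmed as taken for treatment failure are an intercurrent event, so the primary's composite rule would treat part of the rescue outcome as a reason to override it.
- **Low stakes.** Neither endpoint is among the five steps of the hierarchy in SAP 4.6. True, and it sets the severity.

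**Conclusion.** The point holds for rescue therapy as a low-cost improvement. The objective and endpoint are comparative, the planned analysis is not, and the protocol is inconsistent with itself on the method. For emergency care or epinephrine, the plan should either give an interval or say plainly that the endpoint is descriptive.

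Under assumed halvings with 39 per arm, the missing interval would have a half-width of roughly 12 to 21 points. Power for a halving would be 13% to 63% at two-sided 0.05. The estimate would be imprecise, which is a reason to show the interval rather than leave two percentages to speak for themselves. These figures rest on assumed rates, a simple unstratified interval and complete follow-up.

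The primary endpoint, the alpha-controlled hierarchy and the trial's definition of success are not affected.

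**What to change.** 1. **SAP 4.4.2 and protocol Table 7, rescue therapy.** Add the between-arm difference in proportions with a nominal 95% CI, outside the hierarchy. Stratify by region and background H1-antihistamine use as in the primary analysis, or use an unstratified Miettinen-Nurminen interval if events are sparse. The SAP already uses that method for adverse events. State the rule for switching before unblinding.
2. **Event definition.** Count rescue use itself as the event and do not apply the primary endpoint's composite rule. State whether antihistamine and corticosteroid rescue are pooled, and how participants who leave early are counted.
3. **Emergency care or epinephrine.** Give the same nominal interval, or state that the endpoint is descriptive.
4. **Protocol synopsis.** Reconcile its general sentence on binary endpoints with Table 7.

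If the sponsor prefers counts only for rescue therapy, the alternative is to remove the comparison with placebo from that endpoint and call it descriptive. That leaves the reduction objective without an estimate, so it is the weaker choice.

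The cost is a few extra output rows and a short text change, with no new data and no alpha. The downside is an imprecise estimate with no confirmatory status, which should be labelled as such.

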4.5 TERTIARY/EXPLORATORY ENDPOINT(S) ANALYSIS

4.5.1 Definition of endpoint(s)

Additional details are provided below for specific exploratory efficacy endpoints.

- Patient Global Impression of Change (PGIC) of primary acquired chronic inducible ColdU at Week 12 and Week 24
- Change from baseline in Patient Global Impression of Severity (PGIS) of primary acquired chronic inducible ColdU at Week 12 and Week 24

4.5.2 Main analytical approach

Exploratory efficacy endpoints will be analyzed using the same methodology as above for similar data (continuous, proportion).

4.6 MULTIPLICITY ISSUES

To strongly control the family-wise type-I error rate for testing the primary and selected secondary endpoints, hierarchical testing procedure is used. The overall two-sided alpha is 0.01. The comparisons with placebo will be tested based on the hierarchical order below at 2-sided $\alpha = 0.01$.

Order of the testing hierarchy:

1. Proportion of participants with negative ice cube provocation test at Week 24.
2. Change from baseline in local wheal intensity at the provocation site at Week 24 using the wheal intensity Likert scale ranging from 0 to 5 (clinician evaluation).
3. Change from baseline in proportion of cold urticaria symptom free days at Week 24 (exposure-adjusted and measured by ColdUAS).
4. Change from baseline in local itch severity at the provocation site at Week 24 using the Peak Pruritus Numerical Rating Scale (NRS, score 0 to 10) (patient reported).
5. Change from baseline in health-related quality-of-life (HRQoL) as measured by Dermatology Life Quality Index (DLQI) in participants ≥ 16 years old.

4.7 SAFETY ANALYSES

All safety analyses will be performed on the safety population as defined in [Section 3](#), unless otherwise specified, using the following common rules:

- The analysis of the safety variables will be essentially descriptive, and no testing is planned.
- Safety data in participants who do not belong to the safety population (e.g., exposed but not randomized) will be provided separately.

4.7.1 Extent of exposure

The extent of IMP exposure will be assessed by the duration of IMP exposure and compliance and summarized within the safety population.

Duration of IMP exposure

Duration of IMP exposure is defined as last dose date – first dose date + 15 days, regardless of unplanned intermittent discontinuations. If the date of the last dose of IMP is missing, the duration of IMP will be left as missing.

Duration of IMP exposure will be summarized descriptively as a quantitative variable (number, mean, SD, median, minimum, and maximum). In addition, duration of IMP exposure will also be summarized categorically by numbers and percentages for each of the following categories and cumulatively according to these categories:

- >0 and \leq 2 weeks
- >2 and \leq 4 weeks
- >4 and \leq 8 weeks
- >8 and \leq 12 weeks
- >12 and \leq 16 weeks
- >16 and \leq 20 weeks
- >20 and \leq 24 weeks
- >24 weeks and \leq 24 weeks + 3 days
- >24 weeks + 3 days

Additionally, the cumulative duration of IMP exposure will be provided, defined as the sum of the duration of treatment exposure for all participants, and will be expressed in participant years.

Treatment compliance

A given administration will be considered noncompliant if the participant did not take the planned dose as required by the protocol. No imputation will be made for participants with missing or incomplete data.

Percentage of treatment compliance for a participant will be defined as the number of administrations that the participant was compliant divided by the total number of administrations that the participant was planned to take from the first administration of IMP up to the actual last administration of IMP.

Treatment compliance will be summarized quantitatively and categorically: <80%, \geq 80%.

Cases of overdose (defined as at least twice the intended dose during an interval of less than 11 days) are considered an AESI and will be listed as such.

4.7.2 Adverse events

General common rules for adverse events

All adverse events (AEs) will be coded to a lower-level term (LLT), preferred term (PT), high-level term (HLT), high-level group term (HLGT), and associated primary system organ class (SOC) using the Medical Dictionary for Regulatory Activities (MedDRA) version currently in effect at Sanofi at the time of database lock.

The AEs will be analyzed in the following 3 categories:

- Pre-treatment AEs: AEs that developed, worsened or became serious during the pre-treatment period.
- Treatment-emergent adverse events (TEAEs): AEs that developed, worsened or became serious during the treatment-emergent period.
- Post-treatment AEs: AEs that developed, worsened or became serious during the post-treatment period.

Similarly, the deaths will be analyzed in the pre-treatment, treatment-emergent and post-treatment periods.

The primary focus of AE reporting will be on TEAEs. Pre-treatment and post-treatment AEs will be described separately.

An AE with incomplete or missing date/time of onset (occurrence, worsening, or becoming serious) will be classified as a TEAE unless there is definitive information to determine it is a pre-treatment or a post-treatment AE.

If the assessment of the relationship to IMP is missing for an AE, this AE will be assumed as related to IMP. If the severity is missing for 1 of the treatment-emergent occurrences of an AE, the severity will be imputed with the maximal severity of the other occurrences. If the severity is missing for all the occurrences, the severity will be left as missing.

Multiple occurrences of the same event in the same participant will be counted only once in the tables within a treatment phase.

The AE tables will be sorted as indicated in [Table 5](#).

Table 5 - Sorting of AE tables

AE presentation	Sorting rules
SOC, HLGt, HLT and PT	By the internationally agreed SOC order and by alphabetic order of HLGts, HLts and PTs.
SOC, HLT and PT	By the internationally agreed SOC order and by alphabetic order of HLts and PTs.
SOC and PT	By the internationally agreed SOC order and decreasing frequency of PTs a , b
SMQ/CMQ and PT	By decreasing frequency of SMQs/CMQs and PTs a
PT	By decreasing frequency of PTs a

[a](#) Sorting will be based on the SAR231893 dupilumab group

[b](#) The table of all TEAEs presented by SOC and PT will define the presentation order for all other tables (e.g., treatment-emergent SAE) presented by SOC and PT, unless otherwise specified.

Analysis of all adverse events

The overview of TEAE with the details below will be generated:

- Any TEAE
- Any severe TEAE
- Any treatment emergent SAE
- TEAE leading to death
- Any TEAE leading to permanent intervention discontinuation
- Any treatment emergent AESI
- Any treatment emergent other AE of interest grouping
- Any TEAE related to IMP

The AE summaries of **Table 6** will be generated with number (%) of participants experiencing at least one event.

Table 6 - Analyses of adverse events

Type of AE	MedDRA levels
All TEAE	Primary SOC, HLGT, HLT and PT
	Primary SOC and PT
	PT
	Primary and secondary SOC, HLGT, HLT and PT
Common TEAE $\geq 5\%$ in any group)	Primary SOC and PT
TEAE related to IMP as per Investigator's judgment	Primary SOC, HLGT, HLT and PT
	Primary SOC and PT
TEAE by maximal intensity	Primary SOC and PT
Treatment emergent SAE	Primary SOC, HLGT, HLT and PT
	Primary SOC and PT
Treatment emergent SAE related to IMP as per Investigator's judgment	Primary SOC, HLGT, HLT and PT
TEAE leading to permanent intervention discontinuation	Primary SOC, HLGT, HLT and PT
	Primary SOC and PT
TEAE leading to death (death as an outcome of the AE as reported by the Investigator in the AE page)	Primary SOC, HLGT, HLT and PT
Pretreatment AE	Overview ^a
	Primary SOC and PT

^a Will include the following AE categories: any AEs, any serious AEs, any AEs leading to death, any AEs leading to permanent intervention discontinuation

In addition, the exposure adjusted incidence rate of TEAEs by primary SOC and PT will be generated, showing the number of participants with at least one TEAE per 100 patient-years. For participants with an event, patient-years will be calculated up to the first event, and for participants without an event, patient-years will correspond to the length of the TE period.

Risk differences (constructed using the Miettinen and Nurminen method) and hazard ratios (Cox proportional hazards model) for dupilumab versus placebo with corresponding 95% CIs will be provided for the common TEAEs (PT \geq 5% in any intervention group). Participants without an event will be censored at the end of the treatment-emergent period in the Cox model. Forest plots will also be presented.

Analysis of deaths

In addition to the analyses of deaths included in [Table 5](#) the number (%) of participants in the following categories will be provided:

- Deaths during the treatment-emergent and post-treatment periods
- Deaths in non-randomized or randomized but not treated participants

Analysis of adverse events of special interest (AESIs) and other AEs of interest

Adverse events of special interest (AESIs) and other AEs of interest will be selected for analyses as indicated in [Table 7](#). Number (%) of participants experiencing at least one event will be provided for each event of interest. Tables will be sorted as indicated in [Table 5](#).

Table 7 - Selections for AESIs and other AEs of interest

AE Grouping	Criteria
AESI	
Anaphylactic reaction	Anaphylactic reaction algorithmic approach (Introductory Guide for Standardised MedDRA Queries (SMQs) Version 18.1): includes anaphylactic reaction narrow SMQ (20000021) terms and programmatic identification of cases based on occurrence of at least two preferred terms meeting the algorithm criteria occurring within 24 hours of each other. The latter cases identified using the algorithm will undergo blinded medical review taking into account the timing of events relative to each other and to IMP administration for final determination of an anaphylactic reaction or not.
Systemic hypersensitivity reactions	SMQ [20000214] hypersensitivity narrow search and [AE corrective treatment/therapy = 'Y' or Action taken with IMP = 'Drug withdrawn' or Action taken with IMP = 'Drug interrupted'] followed by blinded medical review (documented process) for selection of relevant systemic hypersensitivity events
Helminthic infections	CMQ10544 based on HLGT as "Helminthic disorder"
Any severe type of conjunctivitis	CMQ10498 based on PTs (See Section 5.5) ^a and "Severe" ticked in Adverse Events eCRF page
Any severe type of blepharitis	CMQ10497 based on HLGT as "Lid, lash and lacrimal infections, irritations and inflammations" and "Severe" ticked in Adverse Events eCRF page
Keratitis	CMQ10642 based on the following PTs [keratitis, allergic keratitis, ulcerative keratitis, atopic keratoconjunctivitis, herpes ophthalmic, ophthalmic herpes simplex, corneal infection] ^a

AE Grouping	Criteria
Clinically symptomatic eosinophilia (or eosinophilia associated with clinical symptoms) ^b	CMQ10641 based on HLT = Eosinophilic disorders or PT = Eosinophil count increased
Pregnancy of a female patients entered in a study as well as pregnancy occurring in a female partner of a male patient entered in a study with IMP/NIMP	"Pregnancy" or "Partner Pregnancy" checked on the Pregnancy eCRF page as reported by the investigator
Significant ALT elevation	ALT >5 x ULN in participants with baseline ALT ≤2 x ULN; OR ALT >8 x ULN if baseline ALT >2 x ULN
Symptomatic overdose with IMP	Symptomatic Overdose is answered Yes, with Overdose of IMP answered Yes on AE eCRF.
Symptomatic overdose with NIMP	Symptomatic Overdose is answered Yes, with Overdose of NIMP answered Yes on AE eCRF.
Other selected AE Grouping	
Serious injection site reactions or severe injection site reactions that last longer than 24 hours	HLT = 'Injection site reactions' and either with serious status, or with severe status and (AE end date/time - AE start date/time) ≥24 hours or ongoing
Severe or serious infection	Primary SOC = 'Infections and infestations' and with severe or serious status
Drug-related hepatic disorder	SMQ [20000006] Drug-related hepatic disorders- narrow
Injection site reaction	HLT = 'Injection site reactions'
Malignancy	SMQ [20000091]- Malignant or unspecified tumors narrow
Conjunctivitis (narrow)	CMQ10644 based on the following PTs [Conjunctivitis, Conjunctivitis allergic, Conjunctivitis bacterial, Conjunctivitis viral, Atopic keratoconjunctivitis] ^a
Conjunctivitis (broad)	CMQ10645 based on the following PTs [Conjunctivitis, Conjunctivitis allergic, Conjunctivitis bacterial, Conjunctivitis viral, Atopic keratoconjunctivitis, Blepharitis, Dry eye, Eye irritation, Eye pruritus, Lacrimation increased, Eye discharge, Foreign body sensation in eyes, Photophobia, Xerophthalmia, Ocular hyperaemia, Conjunctival hyperaemia] ^a
Conjunctivitis (FDA)	CMQ10643 based on the following PTs [Conjunctivitis, Conjunctivitis allergic, Conjunctivitis bacterial, Conjunctivitis viral, Eye irritation, Eye inflammation, Giant papillary conjunctivitis] ^a
Keratitis (FDA)	CMQ30102 based on the following PTs [keratitis, allergic keratitis, ulcerative keratitis, atopic keratoconjunctivitis, ophthalmic herpes simplex,] ^a

a The list of terms may be adjusted according to MedDRA version changes

b All cases of Eosinophilia will be included in the analysis, where cases associated with clinical symptoms will be further described in the CSR

The following summaries will be provided:

- All TEAEs, by selected standardized MedDRA query (SMQ)/Customized MedDRA query (CMQ) and PT or by laboratory values (as in alanine aminotransferase (ALT) elevation), showing the number (%) of participants with at least 1 PT,
- The exposure adjusted incidence rate by selected SMQ/CMQ and PT showing the number of participants with at least one TEAE per 100 patient-years.

- All TEAEs, by selected SMQ/CMQ including risk differences and hazard ratios with corresponding 95% CIs.
- For each AESI and other selected AE groupings,
 - Number (%) of participants with any specific TEAE
 - Number (%) of participants with any specific serious AE (regardless of treatment emergent status)
 - Number (%) of participants with any specific treatment emergent serious AE
 - Number (%) of participants with any specific AE leading to death
 - Number (%) of participants with any specific TEAE leading to permanent study drug discontinuation
 - Number (%) of participants with any specific TEAE related to IMP reported by investigator
 - Number (%) of participants with any specific TEAE by maximum intensity, corrective treatment, and final outcome
 - Number (%) of participants with any specific TEAE adjusted by the exposure duration
 - Time to onset of first TEAE and cumulative incidence at specified time points (K-M estimates at Week 12 and 24) and K-M plot may be provided to depict the course of onset over time if the number of events is large enough.
 - Number (%) of participants with injection site reactions by the related injection.
 - Number (%) of participants with different number of injection site reactions.
- In addition, AESIs reported by the investigator in eCRF will be summarized separately.

